Our research team has conducted federally-funded research with Twitter data since 2009 and published a practical tutorial on Twitter mining in the *American Journal of Preventive Medicine* in 2013.²⁵ More recently, through the New York City Hispanic Dementia Caregiver Research Program (R01 NR014430) and a supplement (R01 NR014430-03S2) which focused on understanding mechanisms of social support in Twitter, we have developed a Tweet corpus of >2.6 million English and Spanish Tweets related to dementia caregiving. Moreover, we have applied data science-based cultural analytic techniques for Twitter data mining and developed innovation visualizations for Twitter data.^{17, 19-27} Analyses of Tweet topics detected a high frequency of social support topics and revealed that the sentiments of Hispanic dementia caregivers were primarily negative.^{17, 19-21, 24} Network analyses revealed a high proportion of isolates (i.e., Tweets without responses) and a low proportion of balanced micro-networks, suggesting sub-optimal social support in the networks.^{17-22, 24} We also created a database of >1600 online resources for dementia caregiving.^{17-22, 24} This substantial preliminary work provides evidence that our research team is uniquely qualified to operationalize, implement, and evaluate a Twitter-based social support intervention for Hispanic and Black dementia caregivers.¹⁷⁻³¹

2. Study Design and Statistical Procedures

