Design: The study purpose will be achieved through a quasi-experimental design (non-equivalent 2 group pre and post-test design). The intervention group is **anonymous followers** of two Twitter accounts established: the African American/Black dementia caregiver group and the Hispanic dementia caregiver group. **No personally identifiable information (PII)** under the definition used by the National Institute of Standards and Technology (NIST) such as names, addresses, date of birth, and email addresses will be collected. Instead, we will analyze publicly available Tweet data for network engagement (count of pressing 'like,' 'retweet,' 'reply' button), emotional valence (auto-calculation from Tweet text messages: "this is so helpful"-emotion score +4, "I face many challenges"- emotion score -6), topic changes, the volume of isolates, size and number of communities, and communication types for our outcome variables. To examine general confounders, **three demographic elements (self-reported age, gender, race/ethnicity, un-linkable to name, phone, email, or address)**.

The intervention is summarized in table 1 and comprises the posting of one Tweet per day, replying or directly messaging followers, liking someone else's Tweet, retweeting someone else's Tweet, and a monthly Twitter chat at an established time. The Tweet messages which the IRB will approve from our Aim 2 will be used as an intervention. In addition, Twitter who re-confirm Twitter terms of the agreement, including privacy policy and terms of service (Appendix attached), will be required for this study. If someone decides to follow one of our accounts (i.e., participate in the intervention) and subsequently changes their mind, they can easily change stop following our networks. We will retain our de-identified Twitter followers for our Twitter communities in multiple ways: 1) we will invite caregivers in the dementia caregiver registries (including the NHiRP project), who agreed to be contacted for the future study, developed by Drs. [name] and [name] to follow the relevant Twitter accounts; 2) we will use online advertising function for marketing our Twitter communities using TwitterAds (15 days in Year 3 and 15 days in Year 4); 3) research flyers will be posted in relevant clinics; 4) we will send an invitation via Twitter to the publicly available user IDs (estimated Black user

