Hypothesis 1: Assuming a correlation of pre- and post-test conservatively: reliability of 300 followers will be required. If the correlation between pre- and post is larger, smaller sample sizes are required. Thus, a sample of 300 Blacks and 300 Hispanics is adequate to examine the within-subject change using a paired t-test. The pre-post-test for binary outcomes (% of isolates) is McNemar's test. The minimum required sample size is 208. Thus, the proposed sample sizes will be adequate to test within-group differences.

Hypothesis 2: The total minimum required sample size in each ethnic group (Black and Hispanic) will be 192 for a total of 385 with effect size 0.332 (Cohen's d). Assuming that α =0.05, 1- β =0.80 (power), the total minimum required sample size for the two groups (Black and Hispanic) with effect size 0.1525 (P_0 - P_1) is **318** (**159 per group**).

Data analysis: Extensive processing is required before the actual data analysis, which comprises data science methods and statistical tests for our hypotheses.

Data processing: We will process Twitter data for data analyses through several steps:1) merging of data files in our institutional high performance computing (HPC) environment (Habanero), 2) converting XML to txt file format into a human-readable format for integrity checking, 3) feature selection, and 4) indexing.³⁵

Data science analyses for publicly available de-identified data: We will use a variety of software packages (R, Python, Nvivo, ORA, NodeXL, SAS) for the data science analyses. Since Twitter user demographics and personal data are not directly available, we will apply algorithms to users' Tweets and images to estimate their demographics, including those considered Social Determinants of Health.³⁶⁻³⁹ We will stratify those variables into categories for data analysis procedures as relevant. To answer research question 1, we will descriptively characterize (e.g., #Tweets, # followers, #likes, #retweets) Twitter activity in the two networks. To address the second research question, we will apply Syuzhet sentiment analysis and LDA to characterize negative affect scores and topic models, respectively. For the third research question, we will compute the network measures listed in **Table 1**.

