Emotional valence, expressing topics, and conversational styles in macro-,meso- and micro-level among de-identified Twitter followers will be computed from publicly available Tweet data. Unlike the traditional methods, data science methods such as natural language processing (NLP) and network analyses enable us to detect emotional valence score, changes in topics, volume of isolates, and communication styles without asking the users any questionnaires. The following table summarizes concepts, measurements, units of analysis, and data science analytic methods.

Table 1. Concepts, Measures, Data Science Methods and Units of Analysis

	Concept	Measures [§]	Data Science Methods	Unit
Content	Emotional valence ⁴⁰	Emotional valence score ^{18, 40-45} detected from text data (e.g., "This is so helpful" – emotion score +4, "I am sad"- emotion score -6)	Syuzhet packages 46	***
	Social support (informational, instrumental, emotional, appraisal)	Topic changes in social support ^{17, 19-21}	Topic modeling using hierarchical ⁵¹ and n-gram embedded LDA algorithms ⁵¹⁻⁵⁴	***
ø)	Social network: Macro- level ⁵⁵	The volume of isolates, Network type, Density, Centralization, Cohesiveness 26, 27, 55, 56	Network analysis ¹⁷⁻ 20, 23, 24, 26, 27	***
Structure	Social network: Meso- level ^{57, 58}	Size and number of communities, the volume of the community activities, leaders of community ^{26, 27, 56, 57}	Clauset-Newman- Moore ⁵⁹ Girvan-Newman ⁵⁸	**
	Social network: Micro- level ⁶⁰	16 communication types among triad, number of individual posting activities 26, 27, 56, 57, 60	Triad census analysis ⁶⁰	*

^{*} individual level, ** community level, *** global network level, §all measures in real-time)

Statistical Analyses: Pre-post comparisons will be examined from baseline (3 months pre-intervention) to 3 months (9-12) months after initiation of the intervention. Analyses of pre-post mean differences will be performed using SAS PROC TTEST, PROC Mixed, PROC GLIMMIX, and PROC CATMOD, with adjustments for the correlation within participants induced by repeated measures and for unreliability and missing data treatment. The continuous outcome will be analyzed using SAS PROC TTEST, PROC Mixed, and the binary outcome will

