be analyzed using PROC GLIMMIX or PROC CATMOD (for the McNemar test), depending on the missing data. We will compare measures among the two groups using independent t-tests for continuous variables and Chisquare tests for proportions to test the second hypothesis. Machine learning-based trend analysis 61, 62 will be applied for the continuously detected emotional valence score.

[figure not shown]
3. Study Procedures

Procedure: Publicly available Tweet data (e.g., Tweets, time stamp, self-reported location) from de-identified Twitter followers of our Twitter sites will be obtained from the public database. No personally identifiable information (PII) under the definition used by the National Institute of Standards and Technology (NIST) such as names, addresses, date of birth, and email addresses will be collected. We will analyze publicly available Tweet data for emotional valence (auto-estimation from Tweet messages), topic changes, the volume of isolates, size and number of communities, and communication types for our outcome variables. In addition, three demographic elements (i.e., self-reported age, gender, race/ethnicity, which are un-linkable to their PIIs) will be collected to examine general confounders. Again, no PII will be used or accessed.

Intervention: Two Tweeters, including a bilingual Hispanic, will strictly follow the intervention delivery protocol developed in Aim 2 with guidance from the Tweet-S2 Expert Panel. Daily for 365 days that cross Years 3 and 4, the Tweeters will post a Tweet from the Tweet library to each Twitter community alternating among those related to information, instrumental, emotional, and appraisal support. The Tweeter will also engage in social network activities by replying to, liking, and retweeting messages posted by others. This intervention will be consistently conducted (e.g., time, center brand themes, designs) to enhance intervention fidelity.⁶³ After a Tweet is posted, followers can respond using Twitter functions (e.g., retweet to quote and disseminate our Tweet message, posting a Tweet message to express their after thoughts and questions using @mention, like. and reply function). In addition, the P.I. will examine the archive files to monitor intervention fidelity and reinforce expected behaviors of the Tweeters as needed.

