Publicly available Twitter data collection: During the baseline (3 months pre-intervention) and intervention (365 days crossing Years 3 and 4) periods, we will collect publicly available Tweet messages and associated metadata (e.g., userID, relationship, time stamp, Tweet, Hashtags, Twitter page, geo code, location, type) daily. We will also double-check the data integrity (e.g., incompletely captured data) daily. In terms of missing Twitter data,⁶⁴ we will make an effort to minimize missing data in 3 ways: our designated Tweeters and the P.I. will be available during data collection, two collection tools (NodeXL and NCapture) will be used, and collection of Tweets will be monitored daily to ensure that capture was adequate and with no PII. Figure 1 shows an example of publicly available data collected.

Figure 1. An example of publicly available data collected via NodeXL: Vertex 1 and 2 will be used for macro, meso, and micro level network analyses. Tweet text with no personal identifiers will be used for text analyses, including emotion score calculation and topic modeling.

upon following Twitter networks

will be strictly prohibited and daily monitored/removed.

4. Study Drugs or Devices

Not applicable

5. Study Instruments (e.g., Questionnaires, Interview Outlines, Focus Group Guides) **No direct instrumentations** such as questionnaires (i.e., survey, interview) will be applied for the outcome measurers. Instead, emotional valence, topics, and conversational styles in macro-,meso- and micro-level among **anonymous Twitter followers** will be computed from the publicly available Tweet data. Unlike the traditional methods, data science methods such as natural language processing (NLP) and network analyses enable us to detect emotional valence score, changes in topics, volume of isolates, and communication styles without asking the users. Table 1 above in Data Analyses summarizes concepts, measurements, units of analysis, and data science analytic methods.

6. Study Subjects

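### With no rule for isolates, the number of communities equals real communities plus unconnected users, so it can shift, even in the wrong direction, when only isolates change

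*Combined protocol and SAP*

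**What the plan says.** The table of concepts and measures in section 2 (the second table numbered 1) gives three levels of network outcome. The macro level is "The volume of isolates, Network type, Density, Centralization, Cohesiveness". The meso level is "Size and number of communities, the volume of the community activities, leaders of community", and its method cell reads "Clauset-Newman- Moore ⁵⁹ Girvan-Newman ⁵⁸". The Design paragraph of section 2 and the Procedure paragraph of section 3 list both levels side by side: "topic changes, the volume of isolates, size and number of communities, and communication types for our outcome variables".

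The Figure 1 caption in section 3 says "Vertex 1 and 2 will be used for macro, meso, and micro level network analyses", so one set of vertex data serves every level.

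The data-processing steps in section 2 do not remove isolates. No section sets a minimum community size, says how size is summarised (mean, median or largest), or defines what counts as a tie. Section 1 reports that earlier networks had "a high proportion of isolates (i.e., Tweets without responses"), but gives no percentage.

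**The concern.** Community detection assigns every vertex to some group, and a vertex without ties can only be a group of its own. If such vertices stay in the graph, the meso-level count absorbs the macro-level isolate count, although the plan lists the two as separate outcomes.

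Three readings are then at risk. A pre-post fall in the number of communities could mean only that isolated users gained a tie or stopped following. A real increase in communities could be hidden or reversed. A difference between the Black and Hispanic networks could reflect different isolate shares rather than different community structure.

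**Working it through.** The documents state no number or size of communities, so there is no figure to reproduce. The check is of the mechanism, followed by an illustration on assumed inputs. A real community here means a detected group of two or more connected users.

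**Mechanism.** Let n be users, I isolated users and k real communities.
- Clauset-Newman-Moore merges groups while modularity rises. A vertex of degree zero has no neighbour and gives a gain of zero, so it is never merged.
- Girvan-Newman only splits connected components. An isolate is already a component and stays one.
- Hence number = k + I and mean size = n/(k + I). The median size is 1 once I > k.

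**Simulated confirmation.** Five fixed communities of 8 users, with isolates added as vertices without ties, gave the same result for both algorithms:

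| Isolates | Communities returned | Mean size | Groups of at least 2 | Their mean size |
|---|---|---|---|---|
| 0 | 5 | 8.0 | 5 | 8.0 |
| 10 | 15 | 3.33 | 5 | 8.0 |
| 40 | 45 | 1.78 | 5 | 8.0 |
| 100 | 105 | 1.33 | 5 | 8.0 |
| 200 | 205 | 1.17 | 5 | 8.0 |

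When isolates were coded as self-loops they also stayed singletons under Clauset-Newman-Moore. At 200 isolates they altered the partition of the unchanged core as well (5 real communities became 3).

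**When singletons dominate.** Let s = I/n. Each real community holds at least 2 users, so k ≤ n(1 − s)/2. The singleton share is sn/(sn + k) ≥ 2s/(1 + s), which exceeds one half when s > 1/3, whatever k is. Below one third it depends on k. With 400 users and s = 10%, 10 real communities give 40/50 = 80% singletons, but 120 communities of three give 40/160 = 25%.

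**Illustration.** The 400 users match the size anticipated per group in section 7. The 200 isolates, 10 real communities and the changes below are assumptions.
- Start: 200 + 10 = 210 communities, mean size 400/210 = 1.90. Real communities average 200/10 = 20 users.
- 61 isolates join existing communities: 139 + 10 = 149 (−61/210 = −29%), mean size 400/149 = 2.68. The real number stays at 10, and their mean size grows to 261/10 = 26.1.
- 61 isolates connect and real communities rise from 10 to 15 (+50%): 139 + 15 = 154, a fall of 56/210 = 27%. The sign is wrong.
- 100 isolates leave: 100 + 10 = 110, mean size 300/110 = 2.73, with no real community changed.

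**Range.** The same 61 users joining existing communities gives 130 to 69 (−47%) with 120 isolates at the start, and 290 to 229 (−21%) with 280. Keeping 200 isolates but taking k = 100, the most that 200 connected users allow, gives 300 to 239 (−20%).

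**The case against.** Several objections have force and limit the point.

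- **Growth at fixed network size.** A reader might infer that the measure moves although no real community forms or grows. At fixed size that is wrong: an isolate who gains a tie must join a community or start one. In the 61-user case real communities grow from 20 to 26.1 on average (+30.5%). Only their number is unchanged. The fully artefactual case is isolates leaving. Section 7 anticipates 60% attrition, so departures are realistic, though it does not say who leaves.
- **Duplication.** For the same reason a reader should not conclude that the meso outcome merely duplicates the isolate outcome. Filtered size still responds, properly, when isolates connect.
- **Planned fall in isolates.** A reader might take 0.1525 in section 2 as an expected fall of 15.25 points. It is the Hypothesis 2 effect between the Black and Hispanic groups. No pre-post fall is planned anywhere, so 61 users (0.1525 × 400) is only an illustrative size.
- **Unit.** Section 1 defines isolates on Tweets, and a user with an unanswered Tweet may have other ties. The Hypothesis 1 paragraph points to a user-level outcome ("The pre-post-test for binary outcomes (% of isolates) is McNemar's test"), but no user-level share is given.
- **Undefined graph.** If following, or staff replies and likes, counted as ties and the study account were a vertex, few followers would have degree zero and the problem would shrink. The plan does not say so.
- **Size summary.** The largest community, or the mean over groups of two or more, escapes the distortion. The plan chooses neither.

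None of this removes the identity number = k + I for the graph analysed.

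**Conclusion.** The point holds. Applied as written, the named algorithms return real communities plus isolated users as the number of communities, and a mean or median size is pulled toward 1. The count can change with no change in the real number and can move against it.

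This rests on isolates remaining in the graph, which the shared vertex data and the absence of any exclusion imply. The size of the distortion cannot be read from the documents. On the assumed inputs above, the artefactual fall in the count when 61 isolates join existing communities runs from 20% to 47%. The stronger statement, that the measure mainly re-counts isolates, is certain only above a one-third user-level share, and the documents do not establish that share.

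Priority is modest. Communities are a listed outcome variable, but the two outcomes that section 2 names for the hypotheses and sizes the sample for are emotional valence and percentage of isolates. No test or decision rule is tied specifically to communities.

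**What to change.** In the table of concepts and measures in section 2:

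1. Compute number and size of communities only on detected groups of at least 2 connected users, with at least 3 as a sensitivity analysis. The argument supports excluding singletons; a primary minimum of 3 would also drop connected pairs, so that two isolates who link up would count in neither measure.
2. Name the size summary (for example the mean over those groups, or the largest).
3. State what a vertex and a tie are, and whether the study account is in the graph. If unanswered Tweets are stored as self-loops, remove them before detection, since they can also disturb the partition.
4. Report isolated users only under the macro-level isolate measure.

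The cost is a sentence or two in the plan and a filter in the code, with no new data. The minimum size remains a convention, so the sensitivity result should stand beside the main one.

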Using Twitter to Enhance the Social Support of Hispanic and Black Dementia Caregivers

NCT03865498

IRB approved on 09/13/2021

Study Description

1. Study Purpose and Rationale

The purpose of this study is to evaluate the impact of the Twitter-based intervention on Tweet content and social network structures of Hispanic and Black dementia caregiver networks. The prevalence of dementia is higher in Hispanics and Blacks than non-Hispanic Whites.^{1, 2} Moreover, the caregiving demands in dementia exceed that of other chronic conditions.^{3, 4} Consequently, dementia caregivers often experience social isolation and loneliness and decreased health status, and lower quality of life.⁵⁻⁸ Social support interventions have been demonstrated to help mitigate these issues.^{5, 9} The expansion of social media use, particularly Twitter, among Hispanics and Blacks, ¹⁰⁻¹⁵ offers great promise for improving social support for Hispanic and Black dementia caregivers.¹⁶ In addition, the availability of large volumes of Tweets and associated metadata make it possible to apply innovative data science methods to characterize engagement in a social support intervention and to assess its efficacy over time.¹⁷⁻²⁷ However, analytic frameworks for analyzing content and social network structures in Twitter communities are relatively new and evolving rapidly, and there has been limited use of Twitter for intervention delivery.¹⁶

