IDs-2500, estimated Hispanic user IDs-1800); 4) using the @mention function, we will ask the existing organization and community leaders (e.g., @alzassociation, which has 107K followers) to retweet our invitation messages to reach out their followers; and 5) monthly, we will determine if there are any new key dementia/Alzheimer's Twitter community leaders and send out an invitation to the publicly available user I.D.s.

Table 1. Twitter-based Intervention

Concepts	Tweets	Time	Source	Function	Recipient
Instrumental support	Prepackaged	Daily**	library	Post*	All followers
Appraisal support	Prepackaged	Daily**	library	Post*	All followers
Informational support	Prepackaged	Daily**	library	Post*	All followers
Emotional support	Prepackaged	Daily**	library	Post*	All followers
Engage in social network	Participate in discussion	Daily	Tweeters	Reply,	All followers
				Direct message	(Individual)
Engage in social network	Answer questions from a direct message	Daily	Tweeters	Direct message	An individual
Engage in social network	Answer question from a posted message	Daily	Tweeters	Reply	All followers
Engage in social network	Like followers' Tweets	Daily	Tweeters	Like	All followers
Engage in social network	Retweet relevant Tweets	Daily	Tweeters	Retweet	All followers
Social support	Host 2hr Twitter chat	Monthly	experts	#hashtag	All followers

*posting: open to all followers. **a message daily (e.g., Monday: Instrumental, Tuesday: Emotional, Wednesday: Informational, Thursday: Appraisal, Friday: Instrumental, repeat the sequence to avoid weekday and weekend effect.

The setting, Sample, and Power Analysis: The setting is the U.S. The Sample will be the de-identified flowers of one of the two dementia caregiver networks (Hispanic, Black). Given our recruitment strategies and preliminary work, we anticipate recruiting > 400 de-identified followers in each group. Based on similar Twitter communities (e.g., @ dementiatoday), population N is estimated at 153,300 for 365 days.

For statistical analyses, the necessary sample sizes for hypothesis 1 and hypothesis 2 based upon the power analysis³⁴ are described below. Hypothesis 1 focuses on within-group differences and Hypothesis 2 on between-group differences. The hypotheses include both continuous (emotion valence) and binary (% of isolates) outcome variables.

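### At the plan's own 60% attrition, 400 enrolled per group leaves about 160, below the 300 and 208 given for Hypothesis 1 and the 192 for Hypothesis 2's continuous outcome; conclusions and unit of analysis also need aligning

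*Combined protocol and SAP*

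**What the plan says.** All references are to the combined protocol and SAP.

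- **Purpose and design.** Section 1 aims to "evaluate the impact of the Twitter-based intervention on Tweet content and social network structures". Section 2 (Design) adds: "The study purpose will be achieved through a quasi-experimental design (non-equivalent 2 group pre and post-test design". The intervention group is followers of "two Twitter accounts established: the African American/Black dementia caregiver group and the Hispanic dementia caregiver group". In section 3 (Intervention), "the Tweeters will post a Tweet from the Tweet library to each Twitter community".
- **Hypotheses and tests.** "Hypothesis 1 focuses on within-group differences and Hypothesis 2 on between-group differences". For H1: "Pre-post comparisons will be examined from baseline (3 months pre-intervention) to 3 months (9-12) months after initiation of the intervention". For H2: "We will compare measures among the two groups using independent t-tests for continuous variables", with chi-square tests for proportions.
- **Sizes (section 2).** H1 has 300 per group for the paired t-test and 208 for McNemar's test, without saying whether 208 is per group or in total. The paragraph concludes that the proposed sizes suffice for within-group testing. H2 has 192 per group (Cohen's d 0.332) and 159 per group (difference in proportions 0.1525).
- **Enrolment (section 7).** Attrition of 60% is expected. More than 400 per group is anticipated, but the same sentence caps accrual at 800, or 400 per group, and cites only the 159 per group minimum.
- **Units.** The table of concepts, measures and units lists emotional valence and volume of isolates at global network level.

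**The concern.** The adequacy statement for H1 and the attrition assumption stand in different sections and do not agree. If attrition runs as expected, the paired tests have far fewer pairs than the plan says it needs, and a null H1 result would be weak evidence.

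Two related points affect what an H1 or H2 result would mean. Both networks are treated and no untreated series is described, so the word impact in section 1 goes further than either comparison can. And H1 is sized with tests on follower pairs, while its outcomes are listed at a level where each network has one value per window and there are no pairs.

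**Working it through.** **Inputs.** 400 per group, 60% attrition and 159 per group come from section 7. The figures 300, 208, 192 and 159, with d = 0.332 and difference 0.1525, come from section 2. Alpha 0.05 and power 0.80 appear only in the sentence on the H2 proportion. *Assumed here:* two-sided 0.05 and 80% design power for H1, and a discordant proportion of 0.2 to 0.6 for McNemar's test.

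**1. Reproducing the plan's figures.**
- H1 (300 and 208): cannot be reproduced. The text gives no effect size, correlation value, discordant rate, alpha or power for H1.
- H2 proportion (159): reproduced at 80% power, two-sided, for some base rates only (for example about 0.31 v 0.46, no continuity correction). The base rate is not stated.
- H2 continuous (192): n = 2(z₀.₉₇₅ + z_power)²/d². At 80%: 2 × 7.849/0.1102 = 142.4, so 143. At 90%: 2 × 10.507/0.1102 = 190.7, so 191 (192 with the t distribution). The stated 192 is therefore a 90% power figure.

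**2. Source of the 400.** 159/(1 − 0.60) = 397.5, so 398. This matches 400, which suggests enrolment was sized on the H2 proportion alone.

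**3. Retained followers against each minimum.** 400 × 0.40 = 160.

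| Minimum per group | 160 as a share | Enrolment needed at 60% attrition | Largest attrition 400 can absorb |
|---|---|---|---|
| 159 (H2 proportion) | 101% | 398 | 60.25% |
| 192 (H2 continuous) | 83% | 480 | 52% |
| 208 (H1 McNemar, if per group) | 77% | 520 | 48% |
| 300 (H1 paired t) | 53% | 750 | 25% |

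**4. H1 power at 160 pairs.**
- Paired t (noncentral t): 300 pairs detect a standardised mean change dz = 0.1623 at 80% power. With 160 pairs the noncentrality is 0.1623 × √160 = 2.05 and power is 53%. At 80% power, 160 pairs detect dz = 0.223.
- McNemar: power = Φ[(d√n − 1.96√ψ)/√(ψ − d²)], with ψ the discordant proportion and d the difference. At ψ = 0.3, 208 pairs detect d = 0.106 at 80%. With 160 pairs, (0.106 × 12.65 − 1.96 × 0.548)/0.537 = 0.50, so power is 69%. The result is the same across ψ from 0.2 to 0.6.
- If 300 and 208 were instead set for 90% power, the figures are about 66% and 81%.

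**5. H2 continuous at 160 per group.** Noncentrality 0.332 × √(160/2) = 2.97, and Φ(2.97 − 1.96) gives 84% power. The stated minimum is missed, but power for d = 0.332 stays above 80%.

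**6. Comparing the passages on attribution and units.** H1 contrasts two periods within a treated network, and H2 contrasts two treated networks. Neither separates the intervention from a change that would have happened anyway. The paired t-test and McNemar's test need two values per follower, which a global network measure does not supply.

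**The case against.** **Missing-data models.** Section 2 (Statistical Analyses) also names mixed models, with the choice of binary method depending on missing data, so incomplete records need not be lost. This stands in part. Assume 400 with baseline data, 160 with both windows, data missing at random and correlation r. The equivalent number of pairs is 2/[(1 + r)/160 + (1 − r)/400]. That is 203 at r = 0.3 and 176 at r = 0.7, giving 63% and 57% power instead of 53%. The gap narrows but stays open. A reader might infer that H1 must be run on about half the intended pairs; the text does not commit to that.

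**Correlation.** Section 2 describes its correlation assumption as conservative and says that a larger value needs fewer followers. This stands. For a fixed mean change, pairs needed are proportional to 1 − r, so 160 would match 300 if 1 − r fell to 160/300 = 0.533 of its planned value. True correlations of about 0.47, 0.63 or 0.73 would do it where 0, 0.3 or 0.5 was planned. The text gives no planned value to judge this by.

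**The 208.** If it is a total (104 per group), 160 is enough for McNemar's test. Per group is the natural reading for a within-group test, and the shortfall against 300 remains either way.

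**Stronger readings.** A reader might infer that the lack of a control invalidates H1 and H2. The documents do not support that: the design is openly called quasi-experimental and the hypotheses are framed as differences. Nor does the phrase "to characterize engagement in a social support intervention and to assess its efficacy over time" set an efficacy objective, since it sits in rationale about what Tweet data make possible. A reader might also infer that followers joining or leaving bias the paired tests. Those tests use only followers with both values, so turnover can move network-level summaries but not the paired contrast.

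**Conclusion.** The sample-size statements contradict each other on the plan's own figures. About 160 retained per group covers only the H2 proportion minimum. It is 53% of the H1 paired t-test figure, 77% of the McNemar figure if that is per group, and 83% of the H2 continuous figure. The arithmetic rests on accrual at the 400 cap and attrition of 60%; the 53% and 69% power values also rest on the assumed alpha and design power for H1. They describe the paired tests at the planner's correlation and would improve somewhat under the mixed model.

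The absence of an untreated series calls for a correction of wording. The mismatch between follower pairs and network-level outcomes is a gap in specification that should be closed before analysis.

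**What to change.** 1. **Size and power.** Restate H1 size and power for about 160 retained per group (detectable dz about 0.22 at 80% power), giving the alpha, power, effect size and correlation used and saying whether 208 is per group. Remove the statement that the proposed sizes are adequate for H1 unless this is shown. Reconcile the 192 for the H2 continuous outcome with 160 retained and with the power intended. Keeping 208 or 300 pairs at 60% attrition would instead take 520 or 750 enrolled per group.
2. **Conclusions.** State H1 as within-network change and H2 as between-network difference, and word the purpose in section 1 to match.
3. **Unit and pairing.** Run the H1 paired tests on a per-follower measure, defined for both valence and isolates. Limit them to followers with Tweets in the baseline window, before their own exposure, and in months 9-12. Recruitment continues across Years 3 and 4, so say whether baseline Tweets of later followers will be available. Report network-level measures descriptively on the full network. Restricting those to the same users would drop later followers' replies and could turn answered Tweets into isolates, which section 1 glosses as Tweets without responses.

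**Cost.** Items 1 and 2 are text changes, but the stated H1 power becomes less favourable. Item 3 costs sample: followers without Tweets in both windows leave the paired tests, so 160 is a ceiling on pairs at the planned accrual and attrition.
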